3. OBJECTIVES, ENDPOINTS, AND ESTIMANDS

Table 4: Study ARGX-113-2010 Objectives and Endpoints

Objectives	Endpoints
Primary	
To assess the long-term safety and tolerability of treatment with efgartigimod PH20 SC in participants with BP	
 • Incidence and severity of treatment-emergent AEs, SAEs, and AESIs • Rate of treatment discontinuation because of safety concerns
Secondary	
To assess the long-term efficacy and durability of response with efgartigimod PH20 SC treatment in participants with BP	
 • Proportions of participants achieving^a: 
 – CR while off OCS for ≥ 8 weeks – CR or PR while off OCS for ≥ 8 weeks – CR while on minimal OCS therapy for ≥ 8 weeks. (Minimal OCS therapy is defined as ≤ 0.10 mg/kg/day of prednisone [or an equivalent dose of another OCS]) – CR while off both OCS and efgartigimod PH20 SC for ≥ 8 weeks^b – CR or PR while off both OCS and efgartigimod PH20 SC for ≥ 8 weeks^b • Duration of sustained remission • Proportion of participants who relapse • Time to relapse • Incidence and severity of relapse • BPDAI activity scores, IGA-BP scores, and itch NRS over time • Rate of treatment failure
Additional secondary	
To evaluate the impact of efgartigimod PH20 SC treatment in reducing long-term glucocorticoid-associated toxicity in participants with BP	GTI-related scores, including the GTI-AIS, GTI-CWS, and GTI-SL over time
To evaluate the impact of efgartigimod PH20 SC treatment on QoL in participants with BP	EQ-5D-5L, DLQI, and ABQoL scores over time
To evaluate the PD and immunogenicity of efgartigimod PH20 SC in participants with BP	
 • Percent change from baseline over time for anti-BP180 and anti-BP230 antibody levels • Incidence and prevalence of ADA against efgartigimod (serum levels)

Objectives	Endpoints
Exploratory	
████████████████████ ████████████████████	██ ████████

^a These endpoint criteria can only be met when participants are off rescue therapy.

^b The endpoint applies only to participants who have stopped receiving efgartigimod PH20 SC before protocol amendment 2 is effective.

No estimands have been defined for this OLE study.

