4.2. Scientific Rationale for Study Design

This is an open-label study to evaluate the long-term safety, tolerability, efficacy, QoL, PD, and immunogenicity of efgartigimod PH20 SC in adult participants with BP who have completed ARGX-113-2009, and to evaluate whether participants can achieve sustained remission after stopping efgartigimod PH20 SC treatment.

This study provides the option to all eligible participants to continue (ARGX-113-2009 efgartigimod PH20 SC arm) or initiate (ARGX-113-2009 placebo arm) efgartigimod PH20 SC.

Participants who discontinued IMP (efgartigimod PH20 SC or placebo) and required rescue therapy in ARGX-113-2009 are eligible for this study. They will initiate efgartigimod PH20 SC, and rescue therapy will be tapered or discontinued (refer to Section 6.9.2). IMP will be permanently discontinued if the investigator considers it not to be in the participant's best interest to taper or discontinue rescue therapy or initiate efgartigimod PH20 SC.

Measures are in place to ensure the blinded allocation (efgartigimod PH20 SC or placebo) from ARGX-113-2009 is maintained (Section 6.3 and Section 6.4).

The primary outcome measure is the ongoing safety and tolerability of open-label efgartigimod PH20 SC for approximately 1 year (long-term) after completing ARGX-113-2009. The endpoints aim to demonstrate that efgartigimod PH20 SC is a safe long-term treatment option for BP. The safety and tolerability endpoints for this study are considered to be standard for any clinical study evaluating the safety of an IMP.

Secondary endpoints aim to demonstrate that efgartigimod PH20 SC treatment can provide symptom control and eventually remission for patients with BP, while also reducing the cumulative exposure to OCS. These endpoints are in line with the efficacy endpoints in ARGX-113-2009 and are selected based on the disease terminology described by Murrell et al (2012).¹

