6.9.2. Rescue Therapy Tapering and Discontinuation

Once protocol amendment 2 is effective, newly enrolled and ongoing participants who receive rescue therapy started in ARGX-113-2009 will initiate or continue efgartigimod PH20 SC and rescue therapy will be tapered or discontinued. IMP will be permanently discontinued if the investigator considers it not to be in the participant's best interest to taper or discontinue rescue therapy or initiate efgartigimod PH20 SC (refer to Section 7.1.1).

Guidelines for rescue therapy types are as follows:

- Whole body TCS application should be stopped immediately.
- OCS used as rescue therapy should be tapered according to the instructions in Section 6.9.1.
- Immunosuppressants should be stopped immediately.
- Tetracyclines should be stopped immediately.
- IVIg should be stopped immediately and a 2-week washout period must be implemented before initiating efgartigimod PH20 SC.

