4. EFFICACY, PHARMACODYNAMIC, AND IMMUNOGENICITY ANALYSES

4.1 EFFICACY AND QUALITY OF LIFE

All efficacy endpoints are secondary endpoints in this OLE study and will be evaluated descriptively.

4.1.1 *Available data*

Investigators report the participant's best disease status in episodes with start and end date (no CDA, CDA, CR, PR, Relapse and Treatment failure). Furthermore, BPDAI activity and total score, IGA-BP scores and itch NRS are collected over time.

Quality of life is assessed over time using the ABQOL, DLQI and EQ-5D-5L questionnaires.

The health impact of long-term glucocorticoid use is assessed via the Aggregate Improvement Score (AIS) and Cumulative Worsening Score from the Glucocorticoid Toxicity Index (GTI) and via the GTI Specific List (GTI-SL).

4.1.2 *Derivation rules*

The following endpoints will be derived **for each treatment period separately**:

- 1) Participants achieving CR while off OCS for ≥ 8 weeks (CROff). A participant will be considered a CROff responder if the following criteria are met simultaneously for ≥ 8 weeks (56 days):
 - The participant's reported disease status is CR
 - The participant is off OCS therapy
 - The participant does not receive any rescue therapy (as indicated by the investigator on the eCRF)

Else, the participant will be considered a CROff non-responder. Participants who already have the disease status CR at day 1 of the treatment period or who are off OCS therapy at day 1 of the treatment period or who receive rescue therapy at day 1 of the treatment period, will be considered non-evaluable for this endpoint and will be excluded from this analysis for the corresponding treatment period.

Note: the rules for assessing the OCS dose on a given day are described in section 3.4.2. Similarly, these rules can be used to assess whether rescue therapy is received on a given day. Additionally for rescue therapy, a frequency of PRN (pro re nata, or 'as needed') will be interpreted as a dose of 1 time per week.

- 2) Participants achieving CR or PR while off OCS for ≥ 8 weeks (CR/PROff). A participant will be considered a CR/PROff responder if the following criteria are met simultaneously for ≥ 8 weeks (56 days):
 - The participant's reported disease status is CR or PR (continuously or alternately)
 - The participant is off OCS therapy
 - The participant does not receive any rescue therapy (as indicated by the investigator on the eCRF)

	Statistical Analysis Plan	

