ARGX-113-2010	Final analysis	Final 1.0 of 29APR2025

Else, the participant will be considered a CR/PROff non-responder. Participants who already have the disease status CR or PR at day 1 of the treatment period or who are off OCS therapy at day 1 of the treatment period or who receive rescue therapy at day 1 of the treatment period, will be considered non-evaluable for this endpoint and will be excluded from this analysis for the corresponding treatment period.

- 3) Participants achieving CR while on minimal OCS therapy for ≥ 8 weeks (CRmin). A participant will be considered a CRmin responder if the following criteria are met simultaneously for ≥ 8 weeks (56 days):
- The participant's reported disease status is CR
 - The participant receives ≤ 0.10 mg/kg/day of prednisone (or an equivalent dose of another OCS)
 - The participant does not receive any rescue therapy (as indicated by the investigator on the eCRF). OCS used as rescue therapy will not be considered as rescue therapy if the above criterium of minimal OCS therapy is still met.

Else, the participant will be considered a CRmin non-responder. Participants who already have the disease status CR at day 1 of the treatment period or who are on minimal (≤ 0.10 mg/kg/day) OCS therapy at day 1 of the treatment period or who receive rescue therapy at day 1 of the treatment period, will be considered non-evaluable for this endpoint and will be excluded from this analysis for the corresponding treatment period.

- 4) Participants with treatment failure.

The following endpoints will be derived **for each treatment period separately and additionally for the observation phase:**

- 5) Participants achieving CR while off both OCS and efgartigimod PH20 SC for ≥ 8 weeks (CROff without IMP). A participant will be considered a responder for CROff without IMP if the following criteria are met simultaneously for ≥ 8 weeks (56 days):
- The participant's reported disease status is CR
 - The participant is off OCS therapy
 - The participant is off IMP
 - The participant does not receive any rescue therapy (as indicated by the investigator on the eCRF)

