- 9) Time to relapse:
 - Start date is the first day with status CDA, CR or PR in the treatment period (or observation phase)
 - End date is:
 - the start date of first relapse after having or achieving CDA, CR or PR
 - the end date of the study (end date of last phase), if no relapse
 - Time to relapse (in days) = end date - start date + 1
- 10) For participants with relapse, severity of (first) relapse will be calculated as the BPDAl total score at the onset of relapse (use the first available nonmissing BPDAl total score in the interval of relapse) minus the BPDAl total score at the preceding visit (use the most recent preceding visit for which a nonmissing BPDAl total score is available). Severity of relapse will be categorized as <0 , $0- <10$, $10- <20$, $20- <30$, or >30 .

	Statistical Analysis Plan	
ARGX-113-2010	Final analysis	Final 1.0 of 29APR2025

The following endpoints will be derived **overall**:

- 11) Changes and percent changes from study baseline will be calculated for BPDAI activity and total score.
- 12) Changes from study baseline will be calculated for itch NRS 24-hour average and worst scores.
- 13) C-GTI: Composite Glucocorticoid Toxicity Index comprises the Aggregate Improvement Score (AIS) and the Cumulative Worsening Score (CWS). Details of AIS and CWS derivations are specified in appendix 9.1.
- 14) A total ABQOL score is calculated as the sum of all 17 items score 0 to 3 with higher score indicating worse condition. Missing items are imputed with the average score of the present items if at least half (9) of the items are present. The total score is rounded to the highest integer.
- 15) Changes from study baseline will be calculated for EQ-5D-5L VAS score, DLQI score and total ABQOL score.

4.1.3 *Presentation of results*

Efficacy results will be presented for the ROL analysis set, unless mentioned otherwise. For tables by analysis visit, only the study baseline and last assessment analysis visits will be shown. Other analysis visits will be included in listings.

A frequency tabulation will be created for the number and percentage of participants who achieved CROff at least once during the study (i.e., in any treatment period). The table will also present the number of participants who are evaluable for the endpoint at least once during the study. This number will serve as denominator for the percentage calculation. This table will be based on the SAF analysis set.

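### SAP 4.1.2 drops participants on rescue therapy at day 1 from the CROff, CR/PROff and CRmin denominators, although the protocol only makes being off rescue a condition for response

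*SAP*

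**What the plan says.** SAP 4.1.2 derives three remission endpoints separately for each treatment period: complete remission off oral corticosteroids (CROff, item 1), complete or partial remission off oral corticosteroids (CR/PROff, item 2) and complete remission on minimal oral corticosteroids (CRmin, item 3). A responder must satisfy all criteria together for at least 56 days, and one criterion is that no rescue therapy is taken.

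Each item then names three day-1 states that make a participant non-evaluable for that period: the target remission status is already present; oral corticosteroids (OCS) are already at zero (items 1 and 2) or minimal (item 3); or rescue is being taken. On the third, item 1 removes participants "who receive rescue therapy at day 1 of the treatment period, will be considered non-evaluable for this endpoint and will be excluded from this analysis" of that period, and items 2 and 3 repeat the rule. SAP 4.1.3 tabulates how many participants are evaluable at least once and adds: "This number will serve as denominator for the percentage calculation".

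Protocol Table 4 deals with rescue in footnote a: "These endpoint criteria can only be met when participants are off rescue therapy". Footnote b, attached only to the two endpoints that also require being off efgartigimod, reads: "The endpoint applies only to participants who have stopped receiving efgartigimod PH20 SC before protocol amendment 2 is effective".

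Protocol 4.2 makes participants who stopped study drug and needed rescue in ARGX-113-2009 eligible, and says of them: "They will initiate efgartigimod PH20 SC, and rescue therapy will be tapered or discontinued". Protocol 6.9.2 sets the handling by type of rescue. For corticosteroids, "OCS used as rescue therapy should be tapered according to the instructions in Section 6.9.1". Whole-body topical steroids, immunosuppressants and tetracyclines are to stop at once. For immunoglobulin, "IVIg should be stopped immediately and a 2-week washout period must be implemented before initiating efgartigimod PH20 SC".

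**The concern.** The protocol states what a participant must achieve. The SAP turns part of that into a rule about who is counted. The other two day-1 exclusions remove people who already hold a component of the endpoint and so have nothing to gain on it. The rescue exclusion removes people who have further to go: they must come off rescue and then hold remission for 56 days.

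These participants are treated by design. One who comes off rescue on efgartigimod and then holds complete remission off OCS for eight weeks is a plain success, and one who cannot is a plain failure. Under the SAP neither enters the three proportions for that period. The percentages then describe a narrower population than the protocol's wording implies, and a reader comparing the two documents is not told so.

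**Working it through.** **1. Condition or population?** Footnote a says when the criteria can be met. Footnote b says to whom an endpoint applies. The protocol therefore has a form of words for restricting a population and did not use it for rescue.

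**2. Is the clause needed to enforce footnote a?** No. Items 1–3 already require 56 days without rescue, and anyone who does not reach that is a non-responder. Without the day-1 clause, footnote a is still fully enforced.

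**3. Is the SAP consistent with itself?** Items 5 and 6 (the endpoints also off efgartigimod) carry the same no-rescue criterion but no day-1 rescue exclusion. Item 3 says OCS given as rescue does not count as rescue once the dose is minimal. Yet a participant taking OCS rescue on day 1 is already out: by the rescue clause if the dose is above minimal, by the minimal-OCS clause if not. For that period the allowance has little left to act on.

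**4. Whom does the clause remove that the other clauses do not?**
- CROff and CR/PROff: those on rescue and also taking OCS on day 1 (including OCS as the rescue itself) who are not already in CR (or PR). Anyone on rescue but off OCS is already removed by the off-OCS clause.
- CRmin: those on rescue, above minimal OCS and not in CR. Item 3 does not say whether a zero dose counts as minimal. If it does not, the rescue clause also removes those off OCS.
- Protocol 6.3.2, situation 4B, recognises participants taking efgartigimod together with rescue carried over from the parent study, so the group is foreseen.

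**5. Size.** The plan states no response rate, sample size or number on rescue, so there is no figure to reproduce. Let p be the response among the evaluable, q the response among those removed by this clause alone, and f their share of the widened denominator.

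Proportion with them included = (1 − f)p + fq, so reported minus included = f(p − q).

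With assumed p = 50%, the difference in percentage points is:

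| f | q = 0 | q = 25% | q = 50% | q = 62.5% |
|---|---|---|---|---|
| 5% | 2.5 | 1.25 | 0 | −0.625 |
| 10% | 5.0 | 2.5 | 0 | −1.25 |
| 20% | 10.0 | 5.0 | 0 | −2.5 |
| 30% | 15.0 | 7.5 | 0 | −3.75 |

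Over p = 30% to 70% and f = 5% to 30%, the difference with q = 0 runs from 0.05 × 30 = 1.5 to 0.30 × 70 = 21 points.

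In counts (assumed): 30/60 = 50.0% as reported. Adding 20 participants on rescue, of whom 4 respond, gives 34/80 = 42.5%. With 0 responders it is 30/80 = 37.5%, and with 10 it is 40/80 = 50.0%.

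**6. All day-1 exclusions together.** Assume 100 treated: 50 evaluable at 50% response (25 responders), 20 removed for rescue with no responders, and 30 removed as already in CR or off OCS. If 50%, 70% or 90% of those 30 meet the 56-day criteria, the all-treated figure is (25 + 0 + 15)/100 = 40%, (25 + 0 + 21)/100 = 46% or (25 + 0 + 27)/100 = 52%. The reported 50% can lie on either side.

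**The case against.** The strongest reply is that this is a permissible analysis choice, openly displayed. Protocol 3 defines no estimands, Protocol 9 leaves technical detail to the SAP, and Protocol 9.2 lets the SAP define further populations. All efficacy endpoints are secondary and descriptive, with no hypothesis test. The response tables must show the evaluable number, and rescue use at baseline and by phase is tabulated. This stands as far as it goes: no error rate is affected and the exclusion is not hidden. But the tables do not say how many participants are lost to each clause, no proportion including them is planned, and SAP 6.1 has no entry for the narrowing.

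A reader might infer that response is overstated. The documents do not support that. It requires q < p, and neither value is given. Protocol 4.2 says rescue participants may come from either parent-study arm, so some receive efgartigimod for the first time. Step 6 shows that the other exclusions can pull the figure the other way.

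A reader might also infer that the parent-study failures are dropped. That is too broad. Only those still on rescue on day 1 of a treatment period are removed, and only for that period; someone removed in period 1 may count in period 2. Several rescue types are to be stopped immediately. The relapse, treatment-failure and off-efgartigimod endpoints carry no rescue exclusion.

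Nor does the contrast between tapered OCS rescue and washed-out immunoglobulin carry much weight. For CROff and CR/PROff, a participant whose only rescue was immunoglobulin and who takes no OCS is non-evaluable anyway, through the off-OCS clause.

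**Conclusion.** The point holds as a mismatch of population. Three SAP denominators leave out participants whom the protocol enrols, treats and withdraws from rescue, through a clause that footnote a does not call for and the 56-day criterion makes unnecessary. The loss of their outcomes from these proportions does not depend on the direction of any bias.

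The numerical effect is f(p − q), which overstates response only if those removed respond less often than the rest. That is plausible for people who needed rescue, but not shown. Under the assumed values above it ranges from slightly negative to 21 points. The affected group is narrower than everyone on rescue: for CROff and CR/PROff it is mainly those also taking OCS on day 1. The consequence is confined to descriptive secondary endpoints.

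**What to change.** In SAP 4.1.2 items 1, 2 and 3, delete day-1 rescue as a reason for non-evaluability and keep the 56-day no-rescue criterion, so that these participants are non-responders unless they meet it. If the sponsor prefers to keep the clause, report each of the three proportions a second time with these participants in the denominator on the same terms.

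In either case:
- split the result by rescue on day 1 of the treatment period. The study-baseline flag in SAP 3.2.2 alone is not enough, because the two dates differ for participants who enter through the observation phase, wait for a washout or start a second period;
- tabulate the number non-evaluable for each reason, per endpoint;
- record any retained restriction in SAP 6.1.

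The data are already collected, so the cost is SAP wording and a few table rows. The descriptive proportions may become slightly less favourable. Participants on rescue who are off OCS remain outside CROff and CR/PROff because of the separate off-OCS clause, which this change does not touch.

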2.2 PHASES, PERIODS AND TIME POINTS

2.2.1 *Analysis phases, periods and subperiods*

All assessments and events will be allocated to analysis phases, periods and subperiods as defined in below table.

Table 2: Analysis phase, period and subperiod definition

Phase	Period/Subperiod	Start	End
For participants who don't receive the first IMP administration at the ARGX-113-2010 baseline visit^a, the first phase will be the observation phase.			
For participants who receive the first IMP administration at the ARGX-113-2010 baseline visit^a, the first phase will be the treatment phase.			
Observation		Date of baseline visit in ARGX-113-2010, with 00:00 added as time part	
For participants with a subsequent treatment period:
 
First IMP administration date/time – 1 minute.
 
For other participants:
 
Date of week 48 or EDV visit^c, with 23:59 added as time part.
 
For participants who don't have a week 48 or EDV visit: date of last contact, with 23:59 added as time part.

	Statistical Analysis Plan	
ARGX-113-2010	Final analysis	Final 1.0 of 29APR2025

Phase	Period/Subperiod	Start	End
Treatment	Treatment period 1/ On IMP treatment	
For participants with first IMP administration at the baseline visit:
 
Date of baseline visit in ARGX-113-2010, with 00:00 added as time part.
 
For participants with a previous observation phase and who initiate treatment:
 
First IMP administration date/time
	
For participants with a subsequent Off IMP subperiod:
 
Last IMP administration date/time in treatment period 1.
 
For other participants:
 
Date of week 48 or EDV visit^c, with 23:59 added as time part.
 
For participants who don't have a week 48 or EDV visit: date of last contact, with 23:59 added as time part.

	Treatment period 1/ Off IMP treatment	Last IMP administration date/time in treatment period 1 + 1 minute	
For participants with a subsequent treatment period:
 
First IMP administration date/time in next treatment period – 1 minute.
 
For other participants:
 
Date of week 48 or EDV visit^c, with 23:59 added as time part.
 
For participants who don't have a week 48 or EDV visit: date of last contact, with 23:59 added as time part.

Treatment period 2 is applicable for participants who re-initiate IMP administration after a previous Off IMP subperiod^b.			

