Else, the participant will be considered a non-responder for CROff without IMP. Participants who enter the ARGX-113-2010 study under protocol version 3 (26 April 2024) or 4 (02 May 2024) will be considered non-evaluable for this endpoint. Furthermore, participants who were randomized to the placebo arm in the ARGX-113-2009 study and who enter the ARGX-113-2010 study in the observation phase, will be considered non-evaluable for this endpoint in the observation phase.

- 6) Participants achieving CR or PR while off both OCS and efgartigimod PH20 SC for ≥ 8 weeks (CR/PROff without IMP). A participant will be considered a

	Statistical Analysis Plan	
ARGX-113-2010	Final analysis	Final 1.0 of 29APR2025

responder for CR/PROff without IMP if the following criteria are met simultaneously for ≥ 8 weeks (56 days):

- The participant's reported disease status is CR or PR (continuously or alternately)
- The participant is off OCS therapy
- The participant is off IMP
- The participant does not receive any rescue therapy (as indicated by the investigator on the eCRF)

Else, the participant will be considered a non-responder for CR/PROff without IMP. A participant will be considered non-evaluable for this endpoint using the same rules as for CROff without IMP.

- 7) Duration of sustained remission will be calculated for participants achieving CR while off both OCS and efgartigimod PH20 SC for ≥ 8 weeks (i.e., responders for CROff without IMP) within a treatment period.
 - Start date of sustained remission is 1 week (7 days) after the last IMP administration in the treatment period
 - End date of sustained remission is:
 - the start date of first relapse after achieving CROff without IMP
 - the start date of a (next) treatment period
 - the start date of OCS therapy after achieving CROff without IMP
 - the start date of a rescue therapy after achieving CROff without IMP
 whichever comes first. If none of the above occurs, the participant will be censored at the end date of the study (end date of last phase).
 - Duration of sustained remission (in days) = end date - start date + 1
- 8) Relapse will be evaluated for participants having or achieving CDA, CR or PR during the treatment period (or observation phase). The evaluation period for relapse is till the end of the treatment period (or observation phase) in case a (next) treatment period starts, or else till the end of the study. Only the first relapse in a treatment period (or observation phase) will be considered.

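### As most naturally read, the two off-efgartigimod remission endpoints (SAP items 5-6) stop counting at week 48 or EDV, so a stop after about week 40 is scored a non-response even if remission lasts to week 56

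*SAP*

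**What the plan says.** Protocol Table 4 lists, as secondary endpoints, the proportion achieving "CR while off both OCS and efgartigimod PH20 SC for ≥ 8 weeks" and its CR-or-PR counterpart. Neither carries a week 48 limit. Footnote b confines both to participants who stopped efgartigimod before amendment 2 was effective.

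SAP 4.1.2 makes a participant a responder for item 5 or 6 "if the following criteria are met simultaneously for ≥ 8 weeks (56 days"). One of those criteria is "The participant is off IMP"; the others are disease status, no OCS and no rescue therapy. Anyone evaluable who misses the run is a non-responder. Both items are derived "for each treatment period separately and additionally for the observation phase".

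SAP Table 2 (section 2.2.1) ends the observation phase and the last Off IMP subperiod at "Date of week 48 or EDV visit^c, with 23:59 added as time part". For participants who do not "have a week 48 or EDV visit: date of last contact, with 23:59 added as time part" is used. Follow-up is a separate phase that begins one minute later.

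The neighbouring items go further. Item 8 (relapse) runs to the end of the period if a next treatment period starts, "or else till the end of the study". Items 7 and 9 end at the last phase when no event occurs. Item 7 is calculated only for item 5 responders.

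**The concern.** Items 5-6 are the only response endpoints that require remission after stopping efgartigimod, and Protocol 4.2 gives that question as part of the design rationale. If counting ends at week 48, a late stopper in continuous CR without OCS or rescue is recorded as a failure and drops out of the duration analysis.

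The treatment of follow-up is also asymmetric: a relapse in weeks 48 to 56 counts under items 8-9, while remission days in the same weeks do not count under items 5-6.

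The data to avoid this are already collected. Both schedules of activities mark disease assessment and concurrent BP therapy at EoTP + 8 weeks, and SAP 4.1.1 records disease status as episodes with start and end dates.

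**Working it through.** **Inputs.**
- Required run: 56 days (SAP items 5-6).
- Day numbering: day = 7 × week + 1 (SAP Table 3). Week 40 = 281, week 48 = 337, week 56 = 393.
- Visit windows: week 48 ±7 days; EoTP + 8 weeks ±3 days (Protocol schedules).
- Study length: 48 + 8 = 56 weeks, which reproduces the stated total.

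**Formula.** Table 2 starts the Off IMP subperiod one minute after the last dose, so off-drug days = end day − day of last dose. The latest last dose that permits a response is end day − 56. As a variant, item 7 starts remission 7 days after the last dose; the limit is then end day − 62.

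**Window ending at week 48.**
- Nominal: 337 − 56 = day 281, week 40.0. With the visit 7 days early or late: day 274 to 288, weeks 39.0 to 41.0.
- Variant: 337 − 62 = day 275, week 39.1 (range 38.1 to 40.1).

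**Window ending at week 56.**
- Nominal: 393 − 56 = day 337, week 48.0. With ±3 days on the final visit: day 334 to 340.
- Variant: 393 − 62 = day 331, week 47.1.

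| Last dose | Off-drug days to week 48 | Off-drug days to week 56 |
|---|---|---|
| Week 40 | 56 | 112 |
| Week 41 | 49 | 105 |
| Week 42 | 42 | 98 |
| Week 44 | 28 | 84 |
| Week 47 | 7 | 63 |
| Week 48 | 0 | 56 |

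A participant who stops at week 42 and stays in CR without OCS or rescue has 98 qualifying days by week 56, but items 5-6 see 42.

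**Related cases.** The same cut affects earlier stoppers whose qualifying status begins only after week 40, for example someone in PR at the stop who reaches CR later (item 5). Where a period ends at an EDV held within 7 days of the last dose, it contains at most about 7 off-drug days at any stopping week. However, the protocol distinguishes discontinuation from stopping, so that route lies mainly outside the target group.

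**How many.** The documents give no stop dates, counts or site-level effective dates for amendment 2. If it took effect on its version date (26 Apr 2024, an assumption), a stop at or after week 40 beforehand needs a baseline by 26 Apr 2024 − 280 days = 21 Jul 2023. Later effective dates would move that date later. The group may therefore be small, but so may the endpoint's denominator.

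**The case against.** **The window is inferred.** No sentence in items 5-6 sets a week 48 end. The heading over them also covers items 7-10, and items 7-9 use follow-up, so the treatment period could be just a unit of reporting. SAP 4.1.3 also speaks of achievement at least once during the study. This reading is possible but weaker. Item 8 had to state its extension. SAP 2.2.6 expressly brings follow-up assessments into the preceding treatment period for PD. SAP 4.1.3 glosses achievement as occurring in any treatment period, although that gloss is written for CROff and cannot be literal for items 5-6, which also cover the observation phase. On either reading the evaluation end needs to be stated.

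**A week 48 cut has some logic.** Protocol 6.9 prohibits other systemic BP treatment only through EoTP or EDV. Items 5-6 check only OCS and therapy flagged as rescue, so CR on newly started systemic therapy could pass as drug-free remission. This stands, and the fix must deal with it.

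**Extension alone would harm the endpoint.** Apart from a placebo-arm rule for the observation phase, the SAP makes only version 3 or 4 entrants non-evaluable. Earlier entrants dosed to week 48 under amendment 2 would gain 53 to 59 off-drug days (56 ± 3) simply because the study ended, and could score as responders. This also stands.

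**Follow-up is sparse.** The EoTP + 4 weeks visit applies only to participants receiving efgartigimod at week 48, so these stoppers have one scheduled visit after week 48. True, but 8 weeks is already the visit interval while off drug.

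**The stakes are modest.** These are descriptive secondary endpoints without hypothesis tests, the error lowers the remission rate, and individual data are listed. That limits the severity but does not correct the tabulated proportion or restore item 7 durations.

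**Conclusion.** The point holds as an issue of definition and misclassification. Joining the item 5-6 heading to Table 2, a stop after about week 40 (weeks 38 to 41) cannot yield 56 off-drug days, and a continuing off-drug remission is scored as a non-response with no duration. This rests on reading Table 2 as the evaluation limit, which the contrast with items 7-9 supports.

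Three stronger readings are tempting but unsupported:
- A reader might infer that every late stopper is a structural non-responder. Participants with an earlier qualifying run are already responders, and those with neither a week 48 nor an EDV visit are followed to last contact.
- A reader might spread stop dates evenly over the study and derive a percentage misclassified. Nothing supports even spacing. The restriction to stops before amendment 2 may make late stops less common, and the denominator also includes observation-phase entrants whose off-drug time starts at week 0.
- A reader might conclude that moving the cut to week 56 is enough. Without footnote b and a check on new systemic therapy, that creates false responders.

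The number affected cannot be computed and may be small.

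**What to change.** In SAP 4.1.2, items 5-6:
1. State the evaluation end used for item 8: the end of the treatment period or observation phase if a next treatment period starts, otherwise the end of the study including follow-up. Count the 56 days across the week 48 boundary and let item 7 inherit this definition.
2. Apply footnote b as an evaluability rule, so that participants who did not stop before amendment 2 was effective, including those dosed to week 48, are non-evaluable.
3. Require that no new systemic BP therapy is recorded during the qualifying run.

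If the week 48 cut is intended, say so, and treat those without 56 available off-drug days as non-evaluable instead of as non-responders.

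The cost is a few SAP sentences, a changed date limit, one evaluability flag and one concomitant-therapy check; no new data are needed. The downside is that, for these stoppers, status after week 48 rests on the single EoTP + 8 weeks visit.
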